#### **1.4 Individual Subject Success and Overall Study Success Criteria**

Study success takes into consideration the purpose of the treatment and comparison to a control group as well as the study goals (e.g., superiority or equivalency). All primary evaluation parameters, at minimum, as well as safety information, should be accounted for in the definition of study success.

“Clinically meaningful improvement” (Intervention Responder) is defined for this proposed study as those subjects who 1) achieve no worse than one-eighth of the threshold of 0.44 m/s (1.0 mph) commonly used to represent gait speed associated with community ambulation, and 2) are free of a intervention-related complication in the active control group and the Ekso G intervention group.

Moreover, the Ekso G intervention and the active control group intervention will be considered an overall success if at least 85% of the per protocol population are defined as “Responders” and achieve the criteria specified for “Clinically Meaningful Improvement”.

Individual and overall success rates will be provided at each post-intervention evaluation interval (e.g., 6, 12, and 24 weeks).

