### **1.8 Sample Size Estimate**

Computations for sample size and power are based on effect sizes derived from internal study data and the relevant clinical literature for the primary endpoint. For the Ekso G intervention group, the postulated effect (derived from internal study data) is a mean change from baseline in gait speed of 0.11 m/s, with a corresponding standard deviation of 0.18 m/s. For the active control group, the postulated effect is a mean change from baseline in gait speed of 0.078 m/s (derived from the relevant clinical literature), with a corresponding standard deviation of 0.108 m/s.

The passive control group is postulated to have a mean change of zero with the same standard deviation as active control, or 0.108 m/s. Sample size and power are then computed for both statistical tests cited above: superiority of Ekso G to passive control and non-inferiority of Ekso G to active control.

Under 2:2:1 randomization with a desired power of 80%, the required sample size for superiority of Ekso G intervention to passive control is 38 subjects with evaluable data in the Ekso G intervention group and 19 in passive control (incorporating the 2:1 Ekso G: passive control randomization). For non-inferiority of Ekso G to active control, the groups are of equal size and the required sample size is 37 per group.

Taking the greater of these numbers for each randomized group, total sample size under 2:2:1 randomization is therefore 38 for Ekso G intervention, 38 for active control and 19 for passive control, a total of 95. To account for possible attrition as well as potential variance from the postulated effects, up to 127 subjects in the randomized group will be enrolled.

With the sample size fixed at 38 in both the Ekso G intervention Group and the Active Control Intervention Group, the power estimate for the detection of a significant difference in the **Overall Study Success Rate** is as follows

- The statistical hypotheses are

$H_0$  (Null hypothesis):  $P_E = 0.850$

$H_a$  (alternative hypothesis):  $P_A = 0.550$

- A two group chi-square test with a 0.05 two-sided significance level will have 82% power to detect the difference between a Ekso G Intervention group proportion,  $P_E$ , of 0.850 and the Active Control Group intervention proportion,  $p_A$ , of 0.550 (odds ratio of 0.216) when the sample size in each group is 38.

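### The 85% overall-success rule in SAP 1.4 names both training arms without saying how they combine, and it conflicts with the responder rates planned in SAP 1.8

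*SAP*

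**What the plan says.** SAP 1.4 sets the rule: "the Ekso G intervention and the active control group intervention will be considered an overall success if at least 85" per cent of per-protocol participants are responders. No confidence limit, test or error rate is attached to the 85%. Success rates are to be given at 6, 12 and 24 weeks, but the rule does not name the visit that decides.

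A responder must meet a speed criterion, "achieve no worse than one-eighth of the threshold of 0.44 m/s (1.0 mph"), and must be free of an intervention-related complication. One-eighth of 0.44 is 0.055 m/s. The text does not say that this is a change from baseline.

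SAP 1.8 gives power for what it calls the overall study success rate: "A two group chi-square test with a 0.05 two-sided significance level will have 82% power to detect the difference" between Ekso at 0.850 and an active control proportion "of 0.550 (odds ratio of 0.216) when the sample size in each group is 38". The next paragraph of SAP 1.8 plans the equivalence test on the same kind of success proportions. It assumes an expected difference of 0.00, 16% discordant pairs and 56 per group.

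SAP 1.5 states the overall study hypothesis as a responder comparison with a margin of 15 percentage points. SAP 1.6 ranks that hypothesis above the primary endpoint. Protocol 17.2 and SAP 1.3 state two hypotheses on mean change in 10MWT speed, one against passive control and one against active control.

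SAP 1.1 defines the per-protocol population as completers of any of the three arms with follow-up to the last visit. Its expected size is not given.

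**The concern.** The SAP plans active control at 30 points below a bar that SAP 1.4 appears to apply to it, and plans Ekso exactly on that bar. The stated 82% power concerns a difference between arms. Nowhere do the documents give the chance of meeting 85%.

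Two things are at stake. If the comparator's responder rate counts toward the rule, a weak comparator result can defeat a trial in which Ekso beat passive control and was non-inferior to standard training. And because the unit of the rule is left open, the choice between joint, pooled and per-arm could be made after the results are known.

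**Working it through.** **The plan's own figure.** With p = 0.85 and 0.55, n = 38 per arm, two-sided 0.05:
- pooled proportion 0.70; null SE = √(2 × 0.70 × 0.30 / 38) = 0.1051
- alternative SE = √((0.85 × 0.15 + 0.55 × 0.45) / 38) = 0.0993
- power = Φ((0.30 − 1.96 × 0.1051) / 0.0993) = Φ(0.946) = 82.8%
- odds ratio = (0.55/0.45) / (0.85/0.15) = 0.216

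Both stated values (82% and 0.216) reproduce, so the inputs are read as the SAP meant them.

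**Chance of meeting the 85% rule at those rates.** With 38 in an arm, 0.85 × 38 = 32.3, so 33 responders are needed (32/38 is 84.2%). With two arms pooled, 0.85 × 76 = 64.6, so 65 are needed. Exact binomial tails, arms independent:

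| Reading | True rates 0.85 / 0.55 | True rates 0.85 / 0.85 |
|---|---|---|
| Ekso alone, P(X ≥ 33) | 48.5% | 48.5% |
| Active control alone, P(X ≥ 33) | 0.003% | 48.5% |
| Both arms (product) | 0.0015% | 23.6% |
| Two arms pooled, P(sum ≥ 65) | 0.08% | 52.8% |

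The right-hand column is closer to the zero difference that SAP 1.8 assumes for its equivalence test.

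**Sensitivity to the per-protocol size (not stated).** For selected n from 30 to 56 per arm at 0.85 / 0.55, Ekso alone passes 46% to 61% of the time; the figure moves irregularly because 0.85n is rounded up. The joint chance is at most 0.013% and the pooled chance at most 0.4%.

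**Behaviour around the bar, one arm, n = 38.** A true rate of 80%, below the bar, passes 20% of the time. A true rate of 85% passes 48.5%. A true rate of about 90% is needed for an 80% chance of passing.

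**Responder rates implied by the SAP's means and SDs.** Inputs from SAP 1.8: Ekso change 0.11 (SD 0.18), active control 0.078 (SD 0.108). Assumptions: normal changes, responder threshold a gain of 0.055 m/s, complications ignored.
- Ekso: Φ((0.11 − 0.055) / 0.18) = Φ(0.306) = 62.0%
- Active control: Φ((0.078 − 0.055) / 0.108) = Φ(0.213) = 58.4%

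At 62.0%, P(X ≥ 33 of 38) = 0.07%, so even Ekso alone would almost never pass.

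This step depends on how the threshold is read. If a responder need only avoid a loss of more than 0.055 m/s, the rates become Φ(0.165/0.18) = Φ(0.917) = 82.0% for Ekso and Φ(0.133/0.108) = Φ(1.231) = 89.1% for active control. Ekso alone then passes 29.9% of the time. Neither reading yields 0.850 and 0.550.

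**The case against.** The strongest reply is that SAP 1.4 can be read as a standard applied to each intervention in turn. Ekso then passes about half the time, and the near-certain failure of active control is simply what 0.550 implies. This stands. A reader might infer that the rule as written almost never succeeds, but that follows only on the joint or pooled reading at 0.85 / 0.55, and the SAP does not choose a reading.

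The 0.550 is also one of two planning assumptions. The zero-difference assumption for the equivalence test makes the pooled chance 52.8% if both arms are at 85%. This stands too, although it shows that SAP 1.8 disagrees with itself about the same proportions.

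A reader might take the 85% rule as the SAP's sole definition of trial success. The documents do not support that: the formal overall hypothesis is the 15-point comparison in SAP 1.5, and the 85% rule has no alpha and no place in the sequence of SAP 1.6. The rule nevertheless sits in the section that sets the overall success criteria, and SAP 1.5 ties the study hypothesis to those criteria.

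Any point-estimate bar set at the true rate is met about half the time. That is a general fact, but the SAP chose to plan Ekso at the bar and does not state the consequence.

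The pooled calculation uses two arms, whereas the per-protocol population spans three. Adding passive participants lowers the pooled chance further unless more than 85% of them respond.

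Finally, a reader might argue that the complication-free requirement over 36 sessions by itself keeps the rate below 85%. The documents give no complication rate, and Protocol 9 reports no adverse events with the device to date, so that argument has no basis here and is not relied on.

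**Conclusion.** The rule is defective on each reading, to different degrees. At the SAP 1.8 success rates with 38 per arm, it is met 0.0015% (joint) or 0.08% (pooled) of the time. Per arm, Ekso is close to a coin toss at 48.5%, and active control passes 0.003% of the time. If both arms were truly at 85%, the joint and pooled figures rise to 23.6% and 52.8%. On the SAP's means and SDs, with a 0.055 m/s gain as the threshold and normal changes, Ekso alone would pass about 0.07% of the time.

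The results assume independent arms and a per-protocol size near 38 per arm. The joint and pooled conclusions at 0.85 / 0.55 do not depend on that size over the range tried. The 82% power in SAP 1.8 is correct for what it describes. The fault is the undefined unit of the rule and its conflict with the planned rates. This should be corrected before analysis.

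**What to change.** - Remove active control from the 85% rule in SAP 1.4 and make the rule non-decisional.
- Rest the trial's conclusion on the two primary hypotheses in Protocol 17.2 and SAP 1.3: Ekso superior to passive control, and non-inferior to active control, on week-12 change in 10MWT speed. Protocol 17.2 does not itself define overall success or say that both hypotheses must be met, so the SAP has to state this.
- Report responder proportions per arm with exact 95% intervals as supportive, and say whether 0.055 m/s is a gain from baseline.
- In the same edit, reconcile SAP 1.5 and 1.6, which rank the 15-point responder test above the primary endpoint, and the two expected differences in SAP 1.8 (0.30 and 0.00).
- If an absolute bar is kept, apply it to Ekso only, at week 12. State in SAP 1.8 its probability of being met at the planned rate and per-protocol size (48.5% at a true 85% with n = 38).

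The cost is SAP text across sections 1.4 to 1.6 and 1.8, with no added data or participant burden. The sponsor gives up a headline statement of 85% success.

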### **13. Participant Termination**

Participants will be advised that they may voluntarily withdraw from the study at any time and will be instructed to notify the investigator immediately if they choose to withdraw. Participants may choose to withdraw for any reason and are not obligated to reveal their reason(s) for withdrawal. Should Participants withdraw prior to follow-up completion, they will be asked to complete the final questionnaires if withdrawn prior to the end of the participation period. In addition, Participants may be involuntarily withdrawn by the investigator if the investigator believes it is in the best interests of the Participant (e.g., adverse event that prevents further visits).

If a Participant is lost to follow up, the End of Study CRF must be completed and submitted to the data manager as soon as possible. If a Participant fails to comply with the follow up evaluations, the study site must attempt to contact the Participant at least three times, including once as a registered letter.

In order to minimize loss to follow-up, at the baseline evaluation visit the study coordinator will request that the Participant provide names and contact information of two individuals who have a close relationship with the Participant. The contacts will be utilized in the event that the Participant relocates or cannot be reached by mail or telephone. This information will be treated as confidential and for use by the investigative site only. Every effort will be made to retain Participants for the entire 6 months of follow up.

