## **17. Statistical Methods**

### **17.1 General Principles**

The primary analysis for all baseline characteristics and study outcomes will include all available data for all enrolled subjects. Standard summary statistics will be calculated for all study variables. For continuous variables, statistics will include means, standard deviations, medians and ranges. Categorical variables will be summarized in frequency distributions.

Statistical analyses will be conducted according to the principles of intent-to-treat, under which subjects will be evaluated according to their randomized assignment regardless of the treatment actually received. P-values for tests of superiority will be two-sided and for non-inferiority one-sided, with values less than 0.05 deemed statistically significant.

Statistical analyses will be conducted in SAS version 9.3 or above (SAS Institute, Cary, N.C.), R version 3.2 or above (R Foundation for Statistical Computing, Vienna, Austria, <http://www.R-project.org>) or another validated statistical software package.

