Intent-to-treat population:	Subjects who met the inclusion criteria and were randomized to an intervention arm. Thus, enrolled in the study.
All enrolled population:	Subjects who were enrolled in the study (randomized to an intervention arm) and completed at least one day of the intervention. This group of subjects will be used for safety analysis.
Per protocol population:	All subjects who were enrolled, completed one of the three intervention arms, and were followed out to last follow-up visit after following intervention.

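### The 85% overall-success rule counts only per-protocol completers, so participants who leave because of an intervention-related complication drop out of the denominator instead of counting as failures

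*SAP*

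**What the plan says.** SAP 1.4 sets two conditions for a responder: a gait-speed criterion tied to one-eighth of 0.44 m/s, and that subjects "are free of a intervention-related complication in the active control group and the Ekso G intervention group". The same section then says that the Ekso and active control interventions "will be considered an overall success if at least 85% of the per protocol population are defined as" responders. Rates are to be given at 6, 12 and 24 weeks.

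SAP 1.1 defines the per-protocol population as "All subjects who were enrolled, completed one of the three intervention arms, and were followed out to last follow-up visit after following intervention". It defines the intent-to-treat population as "Subjects who met the inclusion criteria and were randomized to an intervention arm". The 85% rule does not mention the intent-to-treat population.

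Protocol section 13 foresees withdrawal on medical grounds: "Participants may be involuntarily withdrawn by the investigator if the investigator believes it is in the best interests of the Participant", and its example is an adverse event that rules out further visits. Protocol 17.1 states that "Statistical analyses will be conducted according to the principles of intent-to-treat". Protocol 18.1 says that missing values are not imputed, with last observation carried forward as exploratory only. SAP 1.7 keeps discontinued subjects' data up to the point of discontinuation and keeps these subjects under follow-up. It does not say how they count towards the 85%.

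**The concern.** The two halves of SAP 1.4 pull against each other. The responder definition combines efficacy and safety so that a participant harmed by the intervention cannot count as a success. The denominator then removes participants whose harm ended their training or follow-up. The exclusion depends on an outcome that the rule is meant to count, and it occurs after randomisation.

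At stake is the SAP's stated declaration of overall success for the trained interventions. An arm could cross 85% because complication-related leavers were removed, when the same arm would fall short with them counted as the definition implies.

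**Working it through.** **Inputs.** Threshold 85% and per-protocol denominator: SAP 1.4. Up to 127 randomised in 2:2:1, and 38 evaluable per trained arm: SAP 1.8. The number of complication-related leavers, k, is not given anywhere and is an assumption here. I apply the rule arm by arm, also an assumption; the algebra is the same if the arms are pooled.

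**The plan's own figure.** SAP 1.8 states 82% power for success rates of 0.850 against 0.550, 38 per group, two-sided 0.05. With mean proportion 0.70, the null standard error is √(2 × 0.70 × 0.30 / 38) = 0.1051. The alternative standard error is √((0.85 × 0.15 + 0.55 × 0.45) / 38) = 0.0993. Then (0.30 − 1.96 × 0.1051) / 0.0993 = 0.946, which gives 82.8%. The stated figure reproduces. It concerns a between-arm test; the SAP gives no operating characteristic for the 85% threshold itself.

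**Where a leaver goes.** Take a participant who stops training for an intervention-related complication.

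- Responder definition (SAP 1.4): a non-responder, whatever the gait speed.
- Per-protocol set (SAP 1.1): did not complete the arm, so is outside the set.
- Follow-up after discontinuation (SAP 1.7): may continue, but the arm is still not completed.
- Result: absent from both numerator and denominator.

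**Direction.** With r responders among n per-protocol participants and k leavers scored as failures, the rate moves from r/n to r/(n + k). This is lower for every k above zero when r is positive.

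**Size at the enrolment cap.** Per trained arm, 127 × 2/5 = 50.8, about 51. The smallest passing count is 85% of n, rounded up.

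| Leavers k (assumed) | Per-protocol n | Minimum r | Per-protocol rate | Rate of 51 randomised |
|---|---|---|---|---|
| 1 | 50 | 43 (0.85 × 50 = 42.5) | 86.0% | 43/51 = 84.3% |
| 5 | 46 | 40 (0.85 × 46 = 39.1) | 87.0% | 40/51 = 78.4% |

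With only 38 randomised and one leaver, 32/37 = 86.5% becomes 32/38 = 84.2%.

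**How far above the minimum the conclusion still changes.** Passing among 51 needs 44 responders (0.85 × 51 = 43.35; 44/51 = 86.3%). With one leaver, only a count of exactly 43 changes verdict. With five, counts of 40 to 43 out of 46 (87.0% to 93.5%) pass per protocol and fail among those randomised.

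**General form.** If a fraction d of those randomised leave for a complication and everyone else is in the per-protocol set at exactly 85%, the rate among those randomised is 0.85 × (1 − d): 80.8% at d = 5% and 76.5% at d = 10%.

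**The case against.** The strongest reply is that the SAP does not ignore these participants. SAP 1.1 lists individual patient success rates among the analyses to be run in all three populations, including intent-to-treat. Its safety set covers everyone randomised with at least one day of intervention, and SAP 1.3 compares device-related adverse events between the trained arms. Protocol section 12 has an independent board adjudicate serious events. The 85% figure is a descriptive threshold with no test attached, and the protocol's primary comparison of mean gait-speed change does not use it. All of this stands and limits the point. It does not remove it: the 85% declaration names the per-protocol set, and no rule scores leavers as failures in any set.

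Several stronger readings are tempting and not supported.

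- A reader might infer that the rule is blind to harm. It is not. A participant with a complication who completes training and follow-up stays in and counts as a failure.
- A reader might infer that worse complications are less likely to count. That is plausible, but the documents give no data on it.
- A reader might carry the criticism into the 15% margin test of SAP 1.5. That section names no analysis set, so the text shows only a gap.
- A reader might treat the whole step from 51 to 38 as complication losses, giving 33/51 = 64.7% against 33/38 = 86.8%. SAP 1.8 says the extra enrolment also allows for variance from the postulated effects, so this is not a forecast.
- A reader might say the rule breaks a protocol promise covering every analysis. Protocol 17.1 explains intent-to-treat as evaluation by randomised assignment, and the 85% rule is not in the protocol. The two are in tension, and that is as far as it goes.

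**Conclusion.** The concern holds in a limited form. Participants whose training or follow-up ended because of an intervention-related complication are failures under the responder definition and are left out of the 85% denominator. For them the exclusion works in one direction only, upwards.

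At about 51 per trained arm, one such leaver moves a minimum pass from 86.0% to 84.3%, and five move it from 87.0% to 78.4%. These figures rest on an assumed number of leavers and on a result at the minimum passing count, so a change of verdict after one leaver reflects where the example sits. A comfortably higher rate would survive one leaver, though five would overturn any per-protocol rate up to 93.5%.

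This should be fixed, because it affects a stated success declaration and the remedy is cheap. It does not undermine the primary gait-speed analysis or the separate safety comparison.

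**What to change.** In SAP 1.4:

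1. Apply the 85% rule to the intent-to-treat population of each trained arm.
2. Score discontinuation for an intervention-related complication as non-response, whether or not a later 10MWT exists.
3. Score other participants without the 10MWT at the evaluation visit as non-responders for this rule. Add an observed-case sensitivity analysis that leaves those other participants out. This also covers leavers whose reason is unknown, since Protocol section 13 does not oblige them to give one. State that this is a scoring rule for the responder endpoint, so that it is not read as contradicting Protocol 18.1.
4. Keep the per-protocol rate as a supporting figure.

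In SAP 1.5, state which population supplies the success proportions.

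The cost is SAP wording and one added sensitivity analysis. No new data are needed: Protocol section 12 records the relation of adverse events to the device, and SAP 1.7 records the withdrawal reason where known. The downside is a less favourable reported success rate. Item 3 can understate success where data are missing for unrelated reasons, and the observed-case analysis would show by how much. The wording should be settled before outcome data are examined.

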#### **1.5 Overall Study Hypothesis**

The study hypothesis is directly related to the success criteria.

Accordingly, the null hypothesis of the study posits that there is no difference between the success probabilities for the Ekso G intervention and the active control intervention. Therefore, this trial of equivalence compares case success probabilities where the investigational intervention will be considered acceptable only if it can be demonstrated with 95% confidence ( $\alpha = 0.05$ ) that it is, at worst, 15% inferior to the active control intervention ( $\delta = 0.15$ ).

$$H_0: \pi_{\text{Ekso}} - \pi_{\text{Active Control}} \leq -0.15 \text{ vs. } H_a: \pi_{\text{Ekso}} - \pi_{\text{Active Control}} > -0.15$$

where  $\pi_i$  = the probability of subjects who achieve the success criteria that the difference in success probabilities is no more than 15% using the Blackwelder approach to testing equivalence of paired proportions.

